8.1.3 Serious Adverse Event

A serious adverse event is defined as:

1. Unanticipated events possibly related to exposure to study medications such as angioedema, agranulocytosis, hepatic injury, or Stevens Johnson syndrome
2. Other events that are serious AND either related or possibly related to the study which occur at a higher rate than expected in this population
3. Other events that are unexpected AND serious AND either related or possibly related to the study beyond the complications expected in this population

Note that deaths are an expected outcome in this population, and will not be reported as serious adverse events, unless they are determined to be related to study treatment and occur at higher than expected rates in the study population.

8.2 Methods and Timing for Assessing, Recording, and Analyzing, Managing Safety Parameters

The PREVENT CLOT study protocol is the confidential intellectual property of the PREVENT CLOT Principal Investigators, Steering Committee, and the University of Maryland Baltimore and METRC and cannot be used in any form without the expressed permission of the Principal Investigators.

8.2.1 Methods and Timing of Assessment

Adverse events (complications) may be discovered during regularly scheduled visits or through unscheduled patient contacts between visits. Adverse events will be assessed for during the index hospitalization and at the 3 month study visit. They will be recorded on study data forms with an indication of whether or not they are thought to be associated with participation in the study.

8.2.2 AE/SAE Grading and Relationship Assignment

Adverse event grading: Adverse events will be graded using standard criteria. Relationship of event to the study procedure will be determined by the study physician.

GRADE 1 (Mild) Transient or mild discomfort (< 48 hours); no medical intervention/therapy required

GRADE 2 (Moderate) Mild to moderate limitation in activity - some assistance may be needed; no or minimal medical intervention/therapy required

GRADE 3 (Severe) Marked limitation in activity, some assistance usually required; medical intervention/therapy required, hospitalizations possible

GRADE 4 (Life-threatening) Extreme limitation in activity, significant assistance required; significant medical intervention/therapy required, hospitalization or hospice care probable.

Relationship Assignment The relationship of the adverse event to participation in the study will be assessed as either:

Definitely related
Probably related
Possibly related
Unlikely related
Unrelated

8.2.2.1 Adverse Events related to study medications.

The study will capture safety information on LMWH and aspirin, both of which are licensed by the FDA. Complications will be classified as study outcomes (8.1.1), and their relatedness to medication exposure will be assessed by the treating physician.

8.2.3 Recording and Documentation

Sites will maintain source documents including but not limited to laboratory and radiology reports, clinical notes and discharge summaries. After review of initial and final reports by the medical monitor, the events may be reclassified at their discretion.

The PREVENT CLOT study protocol is the confidential intellectual property of the PREVENT CLOT Principal Investigators, Steering Committee, and the University of Maryland Baltimore and METRC and cannot be used in any form without the expressed permission of the Principal Investigators.

8.2.4. Management of Adverse Events

Adverse Events and Serious Adverse Events will be managed according the medical judgment of the treating physician.

8.3 Adverse Event Reporting Procedures

8.3.1 Local Reporting Requirements.

Study sites must always follow and comply with their own local institution's adverse event reporting requirements. Depending on the local requirements, a site may report events locally and not report those events to the METRC Coordinating Center. Each participating site is responsible for ensuring that all local IRB requirements for reporting adverse events (both internal and external) are met.

8.3.2 SAE and Unanticipated Problem Reporting Requirements

All Serious Adverse Events that are unexpected AND related or possibly related to the study must be reported to the Medical Monitor and METRC Coordinating Center within 72 hours of being made aware of the event. The MM will review the event within 48 hours of receiving notice of the event, and will make a determination of relatedness as well as the required action (stopping medication, informing other sites, etc). When necessary, the MM may convene the DSMB to discuss an event.

In addition, Unanticipated Problems (UPs) that are not adverse events must also be reported to the METRC Coordinating Center within 14 calendar days after the event has been discovered. SAEs/UPs will be reported to the METRC Coordinating Center by entering the SAE/UP form into REDCAP. REDCap is programmed to automatically send an email to the Coordinating Center for both SAEs and UPs, and to the Medical Monitor in the case of an SAE.

The Medical Monitor for this study is:

[name], FACP
University of Minnesota
Division of Hematology, Oncology and Transplantation
[name]
[name]
[contact] [contact]
Email: [contact]

LMWH and aspirin are available from multiple sources and have generic versions available so consequently there will be variability in manufacturer.

8.3.3 METRC Coordinating Center Reporting Responsibilities

A Randomized Pragmatic Trial Comparing the Complications and Safety of Blood Clot Prevention Medicines Used in Orthopaedic Trauma Patients Version 11.0 6/1/2021 33

The PREVENT CLOT study protocol is the confidential intellectual property of the PREVENT CLOT Principal Investigators, Steering Committee, and the University of Maryland Baltimore and METRC and cannot be used in any form without the expressed permission of the Principal Investigators.

When an event is determined to be unexpected and related to study medication exposure, the Coordinating Center will send a copy of each report received about the event to all clinical sites, with instructions for each to forward the report to their IRB.

Copies of the report will also be sent to the Study PI, and to the DSMB. The MCC will maintain a list of such events for reporting and review at DSMB and Steering Committee meetings.

8.4 Reporting Pregnancy (Replace text with “N/A” if not applicable)

Pregnancy will always be captured on case report forms as a medical event. LMWH is considered a category “B” medication – to be used only if clearly needed. Aspirin is considered a category “D” medication – adverse reactions have been found in humans – but only in the third trimester, and no participant who is not pregnant at the time of enrollment will still be on study drugs by the final trimester of the pregnancy. If a woman becomes pregnant while on the study medication, the decision to continue study medication will be made by the local treating physician, and the event will be reported in an Unexpected Event Form. Regardless of whether the medication is discontinued or not, the patient will remain in follow-up until the follow-up period is completed and a report on the outcome will be submitted.

8.5 Type and Duration of the Follow-up of Participants After Adverse Events

Study patients who experience an SAE will be followed until resolution of the event, and a final report will be submitted to the medical monitor, the coordinating center and the pharmaceutical company (if applicable).

8.6 Stopping Rules

The DSMB will review the overall progress of the trial in terms of recruitment, data quality, and event frequency and makes a formal recommendation to PCORI at the end of each scheduled meeting as to whether the trial should continue unmodified, continue with protocol modifications or be stopped.

There are two formal interim analyses and one final analysis planned to assess differences between group with respect to death within 90 days of randomization. The first will occur after one-third of enrolled patients are followed for 3 months. The second will occur after two-thirds of enrolled patients are followed for 3 months. At each interim analysis, the DSMB will evaluate whether there is a difference in mortality rates between groups. Specifically, they will assess whether the absolute difference in the risk of death between aspirin and LMWH is different than zero. At each interim analysis, two-sided confidence intervals for the difference in risk for death will be computed. The overall type I error of the interim monitoring procedure will be controlled by using a 99.6% confidence interval at the first interim analysis, 98.8% confidence interval at the second interim analysis and a 96.2% at the final analysis. If probability of dying is 1% in both arms, the probability of falsely declaring harm using this procedure is less than 5%.

The PREVENT CLOT study protocol is the confidential intellectual property of the PREVENT CLOT Principal Investigators, Steering Committee, and the University of Maryland Baltimore and METRC and cannot be used in any form without the expressed permission of the Principal Investigators.

8.7 Premature Withdrawal of a Participant

A participant may be withdrawn from the study without consent if the sponsor decides to end the study. Other reasons for removing a participant without consent may include but are not limited to non-adherence with the protocol and/or therapy, inappropriate behavior towards study personnel, and incarceration.

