10.5 Analysis Plan

Patients will be followed for 3 months post-injury. The primary statistical analysis will follow the intent-to-treat paradigm, which means all patients will be analyzed according to the treatment group to which they were randomized. For the five distinct endpoints under evaluation, no multiple comparison adjustments are planned.

Crossover: We will monitor and calculate crossover rates. Due to insurance issues, we expect greater crossover in the LMWH arm. This will introduce a validity threat by attenuating any effects towards the null. As this is a pragmatic trial and crossover can be expected in the real world, our primary analysis will be based on the intent-to-treat paradigm. However, as a secondary analysis, we will use causal inference techniques (e.g., inverse-probability of treatment weighting, propensity scores) to draw inferences in a counterfactual world without crossover.

Binary Endpoints. Treatment effects for binary endpoints (e.g., death, PE, bleeding/infection) will be estimated using a two-group comparison of proportions; confidence intervals for the absolute risk difference will be reported.

Continuous Endpoints. Treatment effects for continuous endpoints (e.g., satisfaction with care) will be estimated using a two-group comparison of means; confidence intervals for the difference in means will be reported.

Superiority Analyses. Primary Aim 3 will be addressed by computing, at the final analysis, a two-sided 95% confidence interval for the difference in probability of bleeding/infection complications between aspirin and LMWH. Superiority of aspirin will be declared if the upper bound of the confidence interval is less than zero. Alternatively, superiority of LMWH will be declared if the lower bound of the confidence interval is greater than zero. Similarly, Secondary Aims 2 and 3 will be addressed by computing, at the final analysis, a two-sided 95% confidence interval for the difference in mean PSQ-18 and out of pocket costs, between aspirin and LMWH, respectively. Superiority of aspirin will be declared if the lower bound of the confidence interval is greater than zero, with the converse indicating superiority of LMWH.

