7.3 Precautionary and Prohibited Medications and Procedures

In this trial, participants will be randomized to receive either LMWH or aspirin. Participants in this study may not receive any other full dose medication as prophylaxis for anticoagulation or as treatment for a VTE even, nor may they receive additional dosages of aspirin above 81 mg daily. There are no other prohibitions regarding medications management, and participants will be treated according to the local standard of care. Data on specific concomitant medications will be collected (See Section 6.2.1). Should it be determined that the medication the participant was randomized to is no longer clinically appropriate, the study medication will be stopped, the

The PREVENT CLOT study protocol is the confidential intellectual property of the PREVENT CLOT Principal Investigators, Steering Committee, and the University of Maryland Baltimore and METRC and cannot be used in any form without the expressed permission of the Principal Investigators.

research team will record the reason for medication discontinuation, and the participant will continue to be followed through the 3 month follow up.

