8.8 Replacement of a Participant Who Discontinues Study Treatment

Participants who are withdrawn from the study will not count towards the total sample size accrual and will be replaced. Participants who are lost to follow up and have unknown treatment or outcome status will be counted as lost and will not be replaced.

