10.5 Analysis Plan

10.5.1 Intention to Treat Analysis

Patients will be followed for 3 months post-randomization. The primary statistical analysis will follow the intention-to-treat paradigm, which means all patients will be analyzed according to the treatment group to which they were randomized. The primary estimand (difference in all-cause mortality between treatment groups) will be estimated using treatment-specific Kaplan-Meier estimators. The other intention-to-treat estimands will be estimated using treatment-specific cumulative incidence function estimators. Formal definitions of the estimands are provided in the *Statistical Analysis Plan*.

We will test the primary outcome for non-inferiority using the upper bound of a two-sided 96.2% confidence interval compared to the pre-specified non-inferiority margin of 0.75%. If non-inferiority is established at our pre-specified non-inferiority margin, we will test for superiority.

Two-sided 95% confidence intervals will also be presented for all other outcomes, but null-hypothesis significance tests will not be performed.

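### Sections 8.7 and 8.8 permit removal and replacement of participants for non-adherence, which conflicts with the intention-to-treat rule and with the plan's own handling of non-adherence

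*Combined protocol and SAP*

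**What the plan says.** Unless stated otherwise, the text is protocol v11.0.

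- **Section 8.7** lists grounds for taking a participant out of the study: "Other reasons for removing a participant without consent may include but are not limited to non-adherence with the protocol and/or therapy". It gives no decision-maker, threshold, timing or masking, and does not say whether follow-up continues.
- **Section 8.8**, headed "Replacement of a Participant Who Discontinues Study Treatment", says: "Participants who are withdrawn from the study will not count towards the total sample size accrual and will be replaced". It sets no limit by reason. Participants lost to follow-up, by contrast, are counted and not replaced.
- **Section 10.5.1** says of the primary analysis that "all patients will be analyzed according to the treatment group to which they were randomized".
- **Section 10.5.2 and SAP sections 5 and 7.3.5** define non-adherence, including refusal and non-medical crossover, and use it to form a secondary per-protocol subset.
- **SAP section 2** removes two groups from all analyses, late ineligibles and inappropriate enrollments. An independent committee masked to arm makes the final determination.
- **Section 10.1** raises the number randomised from 12,200 to at most 12,400 to allow for those same two groups, with 12,200 in the final analytic sample.
- **Section 7.3** covers a narrower case: "Should it be determined that the medication the participant was randomized to is no longer clinically appropriate, the study medication will be stopped". Such a participant will "continue to be followed through the 3 month follow up".

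**The concern.** Consider a participant who refuses further injections, or who crosses over for a non-medical reason. Section 10.5.2 keeps that person in the primary analysis and leaves them out of the per-protocol subset. Sections 8.7 and 8.8 allow the same person to be removed, uncounted and replaced.

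Adherence is observed after randomisation, the trial is not blinded, and the arms are an injection and a tablet. Both the rate of non-adherence and the kind of patient who becomes non-adherent may therefore differ by arm. Late ineligibility receives masked review; removal under section 8.7 has no such safeguard. The primary test compares mortality of about 1% against a margin of 0.75 points, so what is at stake is whether that comparison remains the randomised one.

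**Working it through.** **1. The plan's own figures.** Inputs are 6,100 per arm, 1.0% mortality in both arms and a margin of 0.75% (sections 5.1 and 10.1), and a two-sided 96.2% interval (section 10.5.1). The one-sided level is 0.019, so z = 2.075.

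- SE = √(2 × 0.01 × 0.99 / 6,100) = 0.001802. Power = Φ(0.0075/0.001802 − 2.075) = Φ(2.088) = 98.2%.
- With 7.5% attrition (about 5,642 per arm), SE = 0.001873 and power = 97.3%. Section 10.1 gives the 7.5% for the original calculation and does not restate it for the revised one.
- At a true 1.00% versus 1.75%, the chance of declaring non-inferiority is 1.9%.
- A simulation of 400,000 trials with the interim looks gives power of 97.1% and 96.3%, false non-inferiority of 2.0%, and a two-sided monitoring error of 4.4%.

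These agree with the stated power above 95% (above 90% in the SAP), false non-inferiority below 2.5% and monitoring error below 5%.

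**2. Size within the enrolment cap.** Let a share f of an arm be deleted, with RR times the mortality of those retained. If the arm's true risk is p, the retained risk is p / (1 − f + f × RR). The documents give neither f nor RR, so both are assumptions.

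Suppose all 200 extra places replace patients removed from one arm: f = 200/6,200 = 3.2%. With true mortality of 1.00% in both arms, that arm's retained risk becomes:

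- RR 0: 1.00/0.9677 = 1.033%, a shift of 0.033 points (0.033/0.75 = 4.4% of the margin).
- RR 2: 1.00/1.0323 = 0.969%, a shift of 0.031 points the other way.
- RR 3: 1.00/1.0645 = 0.939%, a shift of 0.061 points the other way.

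**3. Effect at the margin.** With true risks of 1.00% and 1.75%, and 6,100 retained per arm, false non-inferiority = Φ((0.0075 − d)/SE − 2.075), where d is the difference in retained risks. For 10% removed in each arm at RR 3:

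- Retained risks are 1.00/1.2 = 0.833% and 1.75/1.2 = 1.458%, so d = 0.625 points.
- SE = 0.001926, giving Φ(0.649 − 2.075) = 7.7%.

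| Removed, LMWH / aspirin | RR 2 | RR 3 |
|---|---|---|
| 3.2% / 0 (within cap) | 1.3% | 0.9% |
| 0 / 3.2% (within cap) | 3.5% | 5.9% |
| 5% / 5% | 2.9% | 4.1% |
| 10% / 10% | 4.1% | 7.7% |
| 10% / 3% | 1.2% | 0.8% |
| 3% / 10% | 7.5% | 18.9% |

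At RR 1 every row is 1.9%. For 3.2% removed from LMWH only at RR 0, d = 1.750 − 1.033 = 0.717 points and SE = 0.002120, which gives Φ(0.157 − 2.075) = 2.8%.

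**4. Which rows fit the plan.** Full replacement of 5% needs 12,200/0.95 − 12,200, about 643 extra patients. Replacement of 10% needs 12,200/0.90 − 12,200, about 1,356. The plan allows 200, already earmarked for other groups. The last four rows therefore show how the problem grows and are not forecasts.

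**The case against.** The best defence is that the operative analysis plan already keeps non-adherent patients. Section 10.5.1 is explicit, the per-protocol subset makes sense only if these patients remain in the main analysis, and the SAP does not list them for removal. Section 8.8 speaks of accrual and does not say that data are deleted. Elsewhere, section 5.1.2 uses withdrawal for late ineligibles, so 8.8 might have been meant for them. SAP section 3 will also report reasons for premature discontinuation. If these patients were censored in the Kaplan-Meier estimate, their earlier time at risk would be kept and the deletion arithmetic above would not apply as it stands.

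Much of this stands, and it limits the size of the problem. It does not remove the conflict: nothing restricts 8.7 or 8.8 to late ineligibles, and no text says that patients removed for non-adherence stay in follow-up or analysis. The death-status searches in section 6.3.1 are written for participants lost to follow-up. Censoring at removal would still depend on behaviour that may relate to prognosis.

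A reader might go further in four ways that the documents do not support:

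- **That sites make the decision.** Section 8.7 names no actor.
- **That 7.3 is flatly contradicted.** Its trigger is medication that is no longer clinically appropriate, and non-adherence is not named. The tension runs mainly through the heading of 8.8 and is weaker than the conflict with intention to treat.
- **That the bias favours aspirin.** Version 1.0, section 10.5, said "Due to insurance issues, we expect greater crossover in the LMWH arm", but that text is superseded, and it went on to keep intention to treat as the primary analysis for that reason. More removal from LMWH favours aspirin only if those removed have lower mortality; with higher mortality the sign reverses.
- **That 10% to 20% of an arm would be removed and replaced.** This does not fit the 12,400 cap.

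**Conclusion.** The conflict is real and lies in the current text. Sections 8.7 and 8.8 permit removal and replacement for non-adherence, against section 10.5.1, section 10.5.2, section 10.1 and SAP sections 2, 5 and 7.3.5. Whether such patients are deleted or censored, the primary comparison would be selected on behaviour after randomisation.

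The likely size is small within the cap: about 0.03 points if 200 zero-mortality patients came from one arm, with the same true mortality in both arms. Under other assumed mortality ratios the shift changes sign. False non-inferiority at the margin can then exceed the stated 2.5% or fall below 1.9%. These results assume deletion and a common RR in both arms; censoring was not computed. The clause is a permission, and the documents do not report its use. A reader might infer that the sample size or power is wrong, but both reproduce.

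**What to change.** - **Section 8.7:** remove non-adherence with the protocol or therapy as a ground for withdrawal from study follow-up or analysis. This concerns data collection and analysis only and leaves treatment decisions as they are.
- **Section 8.8:** limit non-counting and replacement to late ineligibles and inappropriate enrollments confirmed by the masked committee, and bring the heading into line.
- **Section 10.5.1 and SAP section 2:** state that all other randomised patients, including any already removed for non-adherence, are analysed in the assigned arm. Seek their 90-day vital status through the existing searches where consent and IRB approval allow.

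The cost is a short amendment, and possibly an IRB extension of the death-status search, whose waiver request is framed for patients lost to follow-up. No new procedures are needed. With these patients retained, power stays at 98.2% (97.3% with 7.5% attrition) and false non-inferiority at the margin stays at 1.9%.

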8.8 Replacement of a Participant Who Discontinues Study Treatment

Participants who are withdrawn from the study will not count towards the total sample size accrual and will be replaced. Participants who are lost to follow up and have unknown treatment or outcome status will be counted as lost and will not be replaced.

